Treatment Satisfaction and Engagement (Aim 3). For patients in the AI-CBT group, we will calculate IVR adherence as we have in the past,⁴⁹ i.e., as the proportion of days during which an assessment was attempted in which one was successfully completed and the number of weeks during which the patient completed at least four out of seven requested IVR reports. Participants' judgments of Treatment Credibility will be assessed using a reliable questionnaire adapted from Borkovec and Nau.⁷⁷ Treatment credibility has been shown to be significantly associated with treatment satisfaction, engagement in treatment, and number of sessions attended. The Pain Treatment Satisfaction Scale of the Patient Outcomes Questionnaire will be used to assess patient satisfaction with various domains of pain care.⁷⁸ This 5-item measure shows good internal consistency and significant associations with staff and patient ratings of patient improvement. Attendance in "Live" Telephone CBT Sessions and Program Dropout In order to understand reasons for treatment dropout, we will attempt to reach samples of patients with low levels of engagement for qualitative interviews. Participants will rate their Continued Skill Use at follow-up for each of the target behaviors emphasized in the CBT program on a 0 (not at all accomplished) to 10 (completely accomplished) scale. As described above, Daily IVR calls will be used to collect data in the AI-CBT condition regarding pedometer measured step-counts, CBT skill practice, and pain-related functioning using pre-recorded questions we have used successfully in our prior studies.

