Intensity of Service Use (Specific Aim 2). We will compare service utilization by category (e.g., CBT therapist time, PCP visits, and pharmacy use) between groups. We will conduct a budget impact analysis⁸⁴ and will include the cost of the intervention (personnel, supplies, CBT therapist training, and IVR fixed/variable costs) as well as costs for specific medical care services likely to be affected. Data from CBT therapists time records will be combined with wage data from the VA Financial Management System to produce estimates of intervention-specific personnel costs. Costs associated with the use of specific medical care services, such as medications, will be obtained from the Decision Support System (DSS) files. Cost analysis will be conducted in accordance with the guidance provided by Mauskopf et al.⁸⁴ including the use of sensitivity analysis and scenarios that allow for varying assumptions about intervention uptake, compliance or component costs. All resource use and cost comparisons will be adjusted for any

observed differences in baseline characteristics. Because costs of resource utilization are usually skewed, alternative modeling techniques (e.g., log-transformed costs, negative binomial regression) will be used.

Intervention Engagement and Satisfaction with Care (Specific Aim 3). As in our prior research,⁴⁹ we will conduct extensive analyses of the process of intervention delivery in both arms. We will monitor the proportion of telephone CBT sessions that are completed, and we will determine the patient and session characteristics associated with patients' reports of skill practice. Patients in the AI-CBT group will report their satisfaction with aspects of the intervention (e.g., whether it provided information useful for achieving behavioral targets), and we will assess the correlation between satisfaction ratings and measures of: intervention engagement, patients' baseline characteristics, and changes in pain-related functioning. Differential dropout across groups will be examined using Kaplan-Meier curves and survival models.

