- (1) Using a randomized non-inferiority design, we will determine whether an **AI adaptive program of telephone-based, personalized and stepped pain CBT that includes brief therapy sessions and automated calls as well as standard one hour treatment sessions (AI-CBT)** has outcomes that are non-inferior compared to a standard CBT program of 10 hour-long sessions;

- (2) We will use a budget impact analysis to quantify the difference in therapist time associated with AI-CBT relative to standard CBT as well as differences in overall ambulatory and inpatient service use;
- (3) We will determine whether AI-CBT results in greater patient satisfaction and engagement, due to its more patient-centered approach that automatically focuses on “what works” for each Veteran.

Sample Size Rationale

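### Aim 3 asks whether AI-CBT gives greater satisfaction and engagement, but the plan specifies no between-arm satisfaction comparison and no session-completion measure defined alike in both arms

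*Combined protocol and SAP*

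**What the plan says.** The Data Analyses Plan (Specific Aims and Hypotheses) states Aim 3 as: "We will determine whether AI-CBT results in greater patient satisfaction and engagement, due to its more patient-centered approach".

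The analysis is in protocol D.9, under Intervention Engagement and Satisfaction with Care (Specific Aim 3), and is repeated under the same heading in the Data Analyses Plan. It has these parts:

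- A general promise: "we will conduct extensive analyses of the process of intervention delivery in both arms".
- Session completion: "We will monitor the proportion of telephone CBT sessions that are completed".
- Satisfaction: "Patients in the AI-CBT group will report their satisfaction with aspects of the intervention", after which "we will assess the correlation between satisfaction ratings and measures of: intervention engagement, patients' baseline characteristics, and changes in pain-related functioning".
- Dropout: "Differential dropout across groups will be examined using Kaplan-Meier curves and survival models".

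On measurement, protocol D.7 (Treatment Satisfaction and Engagement) and its counterpart in the Data Analyses Plan limit one measure to a single arm: "For patients in the AI-CBT group, we will calculate IVR adherence". The same section lists the 5-item Pain Treatment Satisfaction Scale, treatment credibility and continued skill use, with no arm restriction. It does not say at which surveys the satisfaction scale is given.

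**The concern.** To show that satisfaction is greater in one arm, the ratings must be set against those in the other arm. A correlation within AI-CBT can show which AI-CBT patients were more satisfied. It cannot show that they were more satisfied than controls.

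For engagement, IVR adherence has no control counterpart. The proportion of telephone CBT sessions completed could be computed in both arms, but it may not mean the same thing in each. An AI-CBT patient can receive a module as a one-hour call, a 15-minute call or an IVR session, while a control receives only one-hour calls.

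At stake is the satisfaction half of a stated aim, and a sound completion result. If the comparison is not specified now, its instrument, time point, model and denominator will be chosen once data are available.

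**Working it through.** **1. Satisfaction: is a between-arm contrast specified anywhere?**

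- The Aim 3 paragraph in D.9 names ratings by the AI-CBT group and correlations of those ratings. It names no contrast.
- The Aim 2 paragraph just before it does say that utilisation will be compared between groups. The Aim 3 satisfaction text has no such wording.
- The Analysis of Endpoints paragraph extends the primary method to pain intensity, emotional functioning, global perception of change and quality of life. Satisfaction is not named there, nor is it among the secondary outcomes in D.7.
- The same paragraph puts all remaining outcomes on an intent-to-treat basis. That fixes the analysis set, but not the contrast, time point, model or test.

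No between-arm satisfaction analysis is specified.

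**2. Engagement: what is compared between arms?**

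- Dropout is compared by Kaplan-Meier curves and survival models, so this part of the question is answered.
- IVR adherence is defined for AI-CBT only, so no comparison is possible.
- Session completion is to be monitored, with no stated test and no statement on whether IVR sessions count. The documents point both ways:
  - Aim 1 calls the whole AI-CBT programme telephone-based, automated calls included.
  - D.6 lists IVR treatment sessions separately from telephone sessions.
  - The per-protocol definition in D.9 counts IVR and live sessions alike.

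**3. If IVR sessions are not counted.** Both arms have 10 modules over 10 weeks (D.4), so every control has 10 scheduled telephone sessions. In AI-CBT the number is 10 minus the weeks assigned to IVR. Mode is assigned after randomisation according to progress (B.7), and missing step-count or skill reports push a patient towards hour-long sessions (D.10). The AI-CBT denominator therefore depends partly on how well the patient engages with daily reporting. D.1 and D.6 have AI-CBT begin with an IVR session, which would give at most 10 − 1 = 9 telephone sessions. B.7 has all patients begin with a one-hour session. Those sections need to be reconciled.

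**4. Sample size, and an illustration for satisfaction.** The only stated sample size is for the RMDQ. The inputs from D.8 are margin 2, SD 4.5, true difference 0, one-sided 0.025, power 90% and ratio 1.37.

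- Control n = (1 + 1/1.37) × (1.960 + 1.282)² × 4.5² / 2² = 1.730 × 10.507 × 5.0625 = 92.02, rounded up to 93.
- AI-CBT n = 1.37 × 93 = 127.4, rounded up to 128.
- Total 221, as the plan states.

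The documents give no effect size or power for Aim 3. Assume a two-sided 0.05 comparison of a continuous score at 128:93. The standard error in SD units is √(1/128 + 1/93) = 0.1363.

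- Detectable difference at 80% power: (1.960 + 0.842) × 0.1363 = 0.38 SD.
- Detectable difference at 90% power: (1.960 + 1.282) × 0.1363 = 0.44 SD.
- Power = Φ(d/0.1363 − 1.960) is 31%, 60%, 84% and 96% for assumed differences of 0.2, 0.3, 0.4 and 0.5 SD.

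**The case against.** The strongest reply is that the plan already covers more of Aim 3 than the satisfaction sentence suggests.

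- **Dropout is compared across groups, and process analyses are promised in both arms.** This stands. A reader might infer that Aim 3 cannot be concluded at all, but the documents do not support that. Dropout is still only one side of engagement, and the D.7 overview lists the two separately.
- **Satisfaction is not measured only in AI-CBT.** The quoted sentence concerns aspects of the programme, while the Pain Treatment Satisfaction Scale covers pain care generally and carries no arm restriction. This also stands. The gap is in the analysis text, and measurement in both arms appears to be planned. Listing a scale does not specify a comparison, however, and the intent-to-treat rule does not supply one.
- **Telephone CBT sessions may include IVR sessions.** The term is ambiguous, so it cannot be said that IVR sessions are left out. That is itself the reason to define it.
- **A selection bias in completion is not shown.** A reader might infer that the AI-CBT figure mainly describes patients judged to need live contact. But mode assignment is probabilistic (B.7), early enrollees are expected to receive more hour-long sessions (D.6), and missing reports also lead to them (D.10). Neither direction nor size follows. Nor does a smaller number of scheduled calls alone distort a proportion: 4 of 4 and 10 of 10 are both 100%.

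**Conclusion.** The satisfaction half of Aim 3 is comparative, and the plan as written gives no between-arm result for it. The engagement half is partly answered through dropout. Its completion measure lacks a common definition and, on the reading that excludes IVR sessions, rests on denominators that are not comparable between arms.

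This is a defect worth correcting in the third aim, and it does not touch the RMDQ non-inferiority test. The detectable differences of 0.38 and 0.44 SD rest on 128:93 patients with scores and on an assumed two-sided 0.05 level. They illustrate what a comparison could show and do not measure harm from the current text. The conclusion on completion depends on how IVR sessions are counted, which the documents leave open.

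**What to change.** In the Aim 3 analysis paragraph of protocol D.9 and its counterpart in the Data Analyses Plan:

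1. Confirm that the Pain Treatment Satisfaction Scale is given in both arms, and state at which follow-up surveys. Add an intent-to-treat comparison between arms at those surveys: mean difference with 95% confidence interval, adjusted for site and age group.
2. Define session completion in the same way in both arms: the number of the 10 modules completed in whatever mode was assigned, IVR or live, for all randomised patients. Compare it between arms alongside the planned dropout analysis.
3. Label the AI-CBT satisfaction correlations and IVR adherence as descriptive.

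The cost is SAP wording and a little more analysis, provided the scale is given in both arms. One limitation should be stated: the module count treats an IVR module and a live module as equal.

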The AI Engine. Patients' IVR-reported step counts, skill practice, and pain-related functioning will be accessed by the AI engine daily to update the probabilities the system uses to determine which treatment to recommend the next week. We will use a state-of-the-art "contextual bandit" AI algorithm (LinUCB) designed to make careful choices while learning quickly from a patient's treatment response as well as the experience of other patients with similar characteristics (see Appendix A for technical details).⁶⁷⁻⁷⁰ With increased interactions, the system will learn to tailor decisions more effectively to maximize population-level improvements in functioning while minimizing clinician time. In this way, AI-CBT will function similar to the best clinicians, who learn from experience within and across patients. In the context of the trial, this means that patients enrolled early will likely receive less personalized CBT courses that are relatively similar to the standard CBT approach (i.e., a greater number of hour-long sessions), while patients enrolled later will receive services that are more personalized and include a greater frequency of 15 minute therapist sessions and IVR sessions. To maximize the efficiency of this "learning curve": (1) patients will be recruited over a longer period than would potentially be necessary, so that AI-CBT can gain as much experience as possible from patients recruited first and apply that knowledge to patients entering the program later; and (2) patients will be randomized with a greater "N" in the AI-CBT group in order to maximize the system's experience (see power calculation). As part of our evaluation, we will compare outcomes across randomization groups separately for early versus later enrollees, in order to test the hypothesis that AI-CBT will result in greater efficiency over time. These analyses also will allow us to project program benefits if AI-CBT were implemented in VA for thousands of Veterans and multiple years of experience.

CBT Treatment Fidelity will be assessed using the Yale Adherence and Competence Scale (YACS),⁷¹ a validated scale that assesses therapist adherence and competence in delivering manualized behavioral therapy. [name] will rate audiotapes of 30% of all CBT therapist sessions to assure that treatment is consistent with the manual and will provide corrective feedback to the therapists whenever drift occurs.

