Secondary Outcomes. **Global Pain Intensity** will be assessed using the Numeric Rating Scale (NRS-I) an IMMPACT-recommended 11-point numeric rating scale of pain severity.⁷² **Pain-Related Interference** will be measured using the 9-item Interference subscale of the West Haven-Yale Multidimensional Pain Inventory (WHYMPI).⁶⁶ This IMMPACT-recommended measure assesses pain-related interference in daily activities and has demonstrated good internal consistency.⁷² **Depression Symptom Severity** will be assessed using the 21-item Beck Depression Inventory (BDI), a widely used measure with excellent internal consistency and stability.⁶⁰ **The Patient Global Perception of Change** scale is a single item measure that quantifies a participant's overall perception of improvement since beginning treatment and the clinical importance of that improvement. Participants indicate improvement on a 7 point "much worse" to "much better" scale. This is a well-validated measure recommended by IMMPACT.⁷³ Finally, we will use the **Veterans SF-12 to assess health-related quality of life**. This measure has demonstrated good internal consistency and is strongly correlated with socioeconomic status and morbidities.⁷⁵

Resource Use (Aim 2). **Intervention Costs.** Therapists will use a log to record time spent in intervention-related activities for a random 20% of all treatment days. Time records will be combined with wage data from the VA Financial Management System to estimate intervention-specific personnel costs. Technology costs of the AI-CBT program include fixed costs (e.g., software development and computer maintenance) plus variable costs (e.g., minute costs for IVR calls). One-time fixed start-up costs will be reported separately. **VA Inpatient and Outpatient Service Use** data will be obtained from the Musculoskeletal Diagnoses Cohort (MSD), a project currently underway as part of the VA Connecticut Healthcare System's CREATE. The MSD is developing validated algorithms for using VA electronic health record data to identify utilization events, comorbid conditions, receipt of opioid medications, and pain screening results, for patients with pain-related diagnoses. Information on non-VA admissions will be collected by the patient

survey. To mitigate recall bias, we will use a two-time frame method that asks about utilization over the past 6 months and over the past 2 months with more weight given to the shorter timeframe.⁷⁶

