Analysis of Endpoints (addressing Specific Aim 1). We will test for non-inferiority of AI-CBT compared to standard telephone CBT at 12 weeks by comparing the upper limit of the two-sided 95% confidence interval for the difference in the mean RMDQ scores, calculated as AI-CBT minus standard CBT, to the pre-set non-inferiority margin of 2 points in RMDQ and will conclude that AI-CBT is non-inferior if the upper limit is less than 2. Because intent-to-treat analysis can raise the risk of type I error in a non-inferiority trial,⁸¹ we will conduct both a per protocol and intent-to-treat analysis. The "per protocol" group assignment will be defined as completing four or more CBT sessions (either IVR or "live" sessions); however, we will revisit this definition with the Expert Panel prior to the start of the trial. We will declare AI-CBT non-inferior to standard CBT only if AI-CBT is shown to be non-inferior using both the intention-to-treat and per-protocol analysis sets. We expect that RMDQ scores will be normally distributed. If not, we will use transformations to achieve normality. We also will develop a two-level linear mixed-effects model that uses RMDQ follow-up scores at both assessment times (three and six months) as the dependent variables; treatment group, time and the treatment by time interaction as categorical explanatory variables; and baseline RMDQ score as a continuous covariate. If this model shows no significant time by group effect, we can drop the interaction term and test for the time-averaged non-inferiority of AI-CBT compared to standard CBT between 3 and 6 months. This model will also allow for adjustment for design-related factors (e.g., site and age). An unstructured variance-covariance matrix will be used to model the error variance. Secondary outcomes including pain intensity, emotional functioning, global perception of change, and quality of life will be analyzed in a manner similar to that used for the primary outcome. Analyses of all other outcomes will be conducted on an intent-to-treat basis.

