Preplanned Subgroup Analysis. Because AI-CBT will continue to learn patterns in patients' experience throughout the intervention period, we hypothesize that the second 50% of patients randomized will show an even larger difference in clinician time than the first 50%, while still demonstrating non-inferiority in pain-related outcomes. Differences in pain related functioning and in clinician treatment time across treatment groups will be tested in this subgroup analysis after stratifying the sample into early versus later recruits.

Approach to Missing Data. If more than 15% of a covariate is missing, we will use multiple imputation methods based on the SAS MI Procedure. We will check if the pattern of missingness is monotonic (i.e., if patients missing data at 3 months also have missing data at 6 months) and use a Markov chain Monte Carlo method that assumes multivariate normality to impute missing values. We will impute five sets of data and combine the imputed results using the SAS MIANALYZE procedure to obtain a valid estimate of the confidence limit and treatment effect.⁸⁵ When data are missing for items within scale scores, we will use recommended imputation procedures rather than deleting patients list-wise from the analysis.

Mediators and Moderators of Intervention Effects. We will use multivariate modeling to identify the mechanisms through which the intervention achieves effects on outcomes and differential effects across subgroups.⁸⁶ Initial models will include only treatment group as the predictor. Subsequent nested models will introduce potential mediators (such as the number of completed therapist sessions), and we will evaluate changes in the relationship between experimental condition and outcomes before and after covariates are introduced. Analyses of effect moderation will focus on baseline pain severity and comorbid diagnoses using standard approaches to evaluate interactions between these covariates and patients' experimental condition.⁸⁶ Significant interactions will be interpreted by plotting regression lines for predicted outcomes of patients with high and low values of the moderator.

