D.10 Limitations of the Design

The AI engine will only make productive decisions about patients' therapy if valid and reliable information about patients' progress is available. In this respect, the AI-CBT program is identical to clinicians who must rely on patient reports to judge treatment response after a change in management. The AI engine will be programmed to treat dramatic changes in step counts that are likely to be inaccurate as missing data. Missing data on step counts and CBT skill practice will result in conservative choices in the AI-CBT group which in the extreme will leave patients with weekly one hour telephone CBT identical to that received by control patients. In contrast to other applications of reinforcement learning (e.g., purchases among Amazon.com users), the AI engine in this intervention will only be receiving data on a relatively small number of patients and time points. As such, the system will learn relatively slowly for a given patient, especially for patients enrolled in the initial phases of recruitment. We expect that this will lessen the system's ability to maximize cost-savings by offering less resource intensive but equally effective alternatives to extended telephone CBT sessions. As such, the differences in per-patient treatment cost across groups will be a lower bound of what could be expected if the service were implemented in VA with larger samples of patients over longer periods of time. Veterans with chronic pain who have significant comorbidity or are not able to walk will be excluded, limiting generalizability. Sensor technology is continuing to evolve rapidly, and the feedback from IVR+pedometers will likely under-estimate the ability of AI-CBT to personalize treatments using more passive and accurate activity measures yet-to-be-developed.

E. DISSEMINATION AND IMPLEMENTATION PLAN

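### The claim that the clinician-time saving grows with enrollment is tested only by separate arm comparisons in each half, which do not test growth

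*Combined protocol and SAP*

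**What the plan says.** Protocol section D.9, Preplanned Subgroup Analysis, repeated in the SAP under the same heading, states the hypothesis: "we hypothesize that the second 50% of patients randomized will show an even larger difference in clinician time than the first 50" per cent. The later half is also expected to remain non-inferior on pain-related outcomes. The method given is that arm differences in functioning and in clinician time "will be tested in this subgroup analysis after stratifying the sample into early versus later recruits".

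Section D.6 (The AI Engine) says how this is to be done and why: outcomes are compared between arms "separately for early versus later enrollees, in order to test the hypothesis that AI-CBT will result in greater efficiency over time". It adds that these analyses will support projections of benefit to a much larger VA population.

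The plan expects the early saving to be smaller. Section D.6 says "patients enrolled early will likely receive less personalized CBT courses that are relatively similar to the standard CBT approach", and section D.10 says "the system will learn relatively slowly for a given patient, especially for patients enrolled in the initial phases of recruitment".

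**The concern.** The hypothesis compares two savings. The analysis estimates each saving and tests each against zero. Whether the early saving is significant and whether the later one is significant are different questions from whether the later one is larger.

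Two patterns could then be read as support for learning when the saving is constant:

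- both halves significant, which only shows that a saving exists throughout;
- only the later half significant, which can arise by chance and matches the pattern the plan predicts.

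At stake is the trial's distinctive claim, that the algorithm becomes more efficient with experience, and the projection built on it.

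**Working it through.** **Is the contrast specified elsewhere?**

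| Place | Comparison |
|---|---|
| D.9 and SAP, Analysis of Endpoints | Arm by assessment time (3 v 6 months), RMDQ |
| D.9 and SAP, Intensity of Service Use | Arms overall |
| D.9 and SAP, Mediators and Moderators | "Analyses of effect moderation will focus on baseline pain severity and comorbid diagnoses" |
| D.9 and SAP, Preplanned Subgroup Analysis | Arms, after splitting by enrollment half |
| D.6, The AI Engine | Arms, separately in early and later enrollees |

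None is an arm-by-half contrast.

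**Reproducing the plan's sample size.** Inputs from D.8: margin 2, SD 4.5, true difference 0, one-sided alpha 0.025, ratio 1.37:1. SE = 4.5 × √(1/128 + 1/93) = 0.613, and non-central t power is 90.1%. The stated 221 (128:93) reproduces.

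**Inputs for clinician time.** Randomized numbers are 160:118 in D.8, so about 80 v 59 per half. The SAP gives 160:117, which changes nothing material. The documents give no SD for time, so 2, 3 and 4 hours are assumptions, with complete time data and equal variances. Tests are two-sided at 0.05. The SE of an arm difference in one half is SD × √(1/80 + 1/59) = 0.1716 × SD.

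**Constant saving, no learning.** Let p be the power in one half. The two halves are independent, so the chance that both are significant is p², and the chance that only the later one is significant is p(1 − p).

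| True saving in both halves | SD (h) | p | Both significant | Later only |
|---|---|---|---|---|
| 2.5 h | 2 | >0.999 | >99.9% | about 0 |
| 2.5 h | 3 | 0.998 | 99.6% | 0.2% |
| 2.5 h | 4 | 0.951 | 90% | 5% |
| 1 h | 2 | 0.825 | 68% | 14% |
| 1 h | 3 | 0.488 | 24% | 25% |
| 1 h | 4 | 0.304 | 9% | 21% |

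With unequal SDs (4 in AI-CBT, 2 in control), the 2.5-hour saving is significant in both halves 99.5% of the time. Section B.9 projects AI-CBT at under half the clinician time of ten one-hour sessions, a saving above 5 hours. At that size both halves are significant almost always, whether or not the saving grew.

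**The direct contrast.** Interaction SE = SD × √(2/80 + 2/59) = 0.2427 × SD. The overall arm comparison has SE = SD × √(1/160 + 1/118) = 0.1213 × SD, so the ratio is 2.0. The 95% half-width is 1.969 × SE.

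| SD (h) | 95% CI half-width (h) | Change detectable with 80% power (h) | Power for a 2 h change |
|---|---|---|---|
| 2 | 0.96 | 1.4 | 98% |
| 3 | 1.43 | 2.0 | 78% |
| 4 | 1.91 | 2.7 | 54% |

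In simulation (20,000 runs) with a constant saving, the interaction test rejected 5.0% to 5.3% of the time.

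**RMDQ in one half.** Evaluable numbers are 128:93 halved, 64 v 46.5. SE = 4.5 × √(1/64 + 1/46.5) = 0.867, the 95% CI is ±1.72, and power against the "pre-set non-inferiority margin of 2 points in RMDQ" is about 63%.

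**The case against.** The strongest reply is that this is an omission and not a wrong test. D.9 gives no model and no rule for declaring learning, the two savings would be reported side by side, and the moderator paragraph allows for interactions generally without limiting them to the two covariates it names. This does not rescue the plan. D.6 presents the separate comparisons as the test of greater efficiency over time, and nothing supplies the contrast.

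Three smaller points stand in part.

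- Stratifying is the right way to examine non-inferiority on RMDQ within the later half. The 63% power is a separate caution about a small subgroup and does not bear on the time hypothesis.
- The later-only figures use a 1-hour saving, well below what B.9 projects. At 2.5 hours the later-only chance is 5% or less, and above 5 hours it is negligible. At the projected size the problem is that two significant results are uninformative.
- D.7 (Resource Use) says "Therapists will use a log to record time spent in intervention-related activities for a random 20% of all treatment days". If only those days supply patient-level time, the interaction will be less precise than shown.

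The scale also matters, because D.9 foresees skewed resource costs and alternative models, and an interaction in hours need not agree with one on a log scale. That is a reason to name the scale in advance.

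**Conclusion.** The concern holds. Followed as written, the analysis can neither confirm nor refute a growing saving. That conclusion is a matter of logic and does not depend on the assumed SDs or savings. The percentages do: they are illustrations that assume complete time data and equal halves, with equal SDs except in the one unequal-SD case.

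The effect is confined to the learning claim and the projection drawn from it. This is a preplanned subgroup hypothesis and not one of the three specific aims, so the change is one the sponsor should make rather than one on which the trial's main conclusion depends.

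**What to change.** Add to the SAP, under Preplanned Subgroup Analysis:

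> The learning hypothesis will be tested in the full sample by the arm-by-enrollment-half interaction (first versus second 50% randomized) for clinician time in hours, adjusted for site and age stratum. The interaction will be reported with a 95% CI, alongside the early and late arm differences. Continuous enrollment order will be a supporting analysis. Within-half comparisons of clinician time are descriptive for the learning claim.

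For RMDQ, keep the later-half comparison, report it as an estimate with a 95% CI against the 2-point margin, and note its limited power. Align D.6 with this wording, and state whether patient-level time comes from all treatment days or only the logged ones.

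The cost is wording: no extra patients or visits are needed, and randomization order is already held. The price is precision. The interval is about ±1.0 to ±1.9 hours at the assumed SDs, and wider if time is known only for the logged 20% of days. A significant interaction would show that the saving changed over enrollment, not that the algorithm's learning caused the change.
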